## 6. PARTICIPANT IDENTIFICATION AND RECRUITMENT

### 6.1. Saving Babies Lives Training Programme

#### 6.2. Study Participants

The Saving Babies Lives Programme will be aimed at government health care staff working in the community (VHSG), at HC (nurses and midwives) and at the referral hospital (doctors and nurses)

#### 6.3. Inclusion Criteria

- Staff members chosen by the Provincial Health Director to attend the programme

#### 6.4. Exclusion Criteria

- Not applicable

#### 6.5. VHSG Baby Health Meetings

#### 6.6. Study Participants

- Two VHSG from villages served by each HC cluster
- Adults (aged 18 years or older)

## **6.7. Inclusion Criteria**

- Work as a VHSG
- Live in a village served by a chosen HC
- Are able to commit to attend meetings regularly
- Give consent to participate in the meetings

## **6.8. Exclusion Criteria**

- Refusal to participate
- Be from a village where two members have already been chosen

# **7. STUDY PROCEDURES**

## **7.1. Saving Babies Lives Programme**

### **7.2. Recruitment**

Not applicable

## **7.3. Screening and Eligibility Assessment**

Not applicable

## **7.4. Informed Consent**

Not applicable

## **7.5. Discontinuation/Withdrawal of Participants from Study**

- Each participant has the right to withdraw from the SBLP at any time.
- The reason for withdrawal will be recorded in the teaching attendance log book.

## **7.6. VHSG Baby Health Meetings**

### **7.7. Recruitment**

The Saving Babies Lives Team (SBLT) will visit all health centres and give a presentation about the project. All VHSGs will be invited to take part in the meetings

Each VHSG will be approached (face-to-face) and asked whether they give consent to be in the BHM.

Demographic data will be collected from all VHSG. A short questionnaire administered to assess knowledge on neonatal health, attitudes towards neonatal health and their practice as VHSG. This questionnaire will be repeated on an annual basis to observe changes in responses over time.

If a participant leaves the group, their replacement VHSG will be approached and asked to join the group.

## **7.8. Informed Consent**

Formal written consent for the VHSG to participate in the BHM will not be taken. This decision has been made for the following reasons:

1. Consent will be inferred by the fact that the VHSG is attending the meeting. The individuals will only take an active role in the discussion if they wish to
2. The Provincial Health Director of PVH regards attendance at the BHM as being part of the normal role of the VHSG and has requested that no special procedures be undertaken

## **7.9. Discontinuation/Withdrawal of Participants from Study**

Each participant has the right to withdraw at any time. In addition, the Investigator may discontinue a participant from the study at any time if the Investigator considers it necessary for any reason including:

- Non-attendance at three or more meetings within one year
- Withdrawal of Consent

The reason for withdrawal will be recorded

## **8. STATISTICS AND ANALYSIS**

### **8.1. Description of Statistical Methods**

#### ***VHSG Baby Health Meetings***

Summary forms from the BHM will be translated into English. Ten percent of data will be double translated and transcribed and the two versions compared for errors. The data will be exported into a qualitative software package (N-Vivo 10 (QSR International, Cambridge, MA). After data entry an analytical framework will be developed to identify common and emerging themes, which will then be coded. Once the codes have been developed they will be applied to the whole data set for interpretation of the data. Quantitative data will be used to contextualise the qualitative data [14-16]. Ethnographic and content thematic analysis will be performed on the data generated by the BHM. This will focus on process evaluation and outcome evaluation. The Medical Research Council guidelines for evaluating complex interventions will be used as a guide [24].

#### **Primary Outcome:**

- Factors associated with the success or failure of the engagement process
  - Factors to explore:
    - Involvement of group members in the meeting
    - Cohesiveness of the group
    - Taking message back to the community
    - Acceptability of the process
    - Appropriateness of group members
    - Factors influencing the ability / inability of the VHSG to implement suggested interventions

#### **Secondary Outcomes:**

- Changes in the VSHG's knowledge, attitudes and practices in neonatal health over time
- VHSG's perceptions of neonatal health issues in rural Cambodia

- Interventions suggested to improve neonatal care and reasons behind them
- Acceptability of the groups to the community / health providers / community leaders
- Acceptability to the group
- VHSG's perception of the effectiveness of interventions
- Involvement of community members with the program

### ***Perinatal Mortality***

The analysis will be performed by intention to treat; mothers and their infants who began the study as residents of one cluster will remain in that group even if they move to another cluster.

#### **Primary Outcome:**

1. Perinatal mortality rate will be described by hazard rate and 95% confidence interval (CI) separated by groups. Survival between groups will also be described using Kaplan-Meier plot. Log-rank test will be used for univariate comparison of survival. We will also describe median time to perinatal death with 95% CI in each group from Kaplan-Meier plot.

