### **3. BACKGROUND AND RATIONALE**

Globally the proportion of childhood deaths that occur in the neonatal period is increasing [1]. Since 1990 there has been a 47% reduction in deaths in children less than five years of age [2]. However, this rate of reduction has not been seen in infants four weeks of age or younger (neonates). It is estimated that 2.9 million neonates die each year, with one million of these occurring on the first day of life [3]. Neonatal mortality now makes up 44% of all deaths in children younger than five years [3]. The reasons why the fall in neonatal mortality has not mirrored that seen in children mortality, is complex and one that is not well explored in the literature.

Cambodia has met most targets of the 4th and 5th Millennium Development Goals, reducing child mortality and improving maternal health by investing in health systems [4, 5]. However, the Sustainable Development Goals call for further improvements and Cambodia continues to fall behind its neighbouring countries in reducing neonatal mortality [6].

One proposed explanation is that interventions that have been successfully employed to reduce childhood death do not reach the community and it is in the community where most neonates die [7, 8]. Another pervasive perceived barrier to providing neonatal care, particularly in remote and rural areas, is the misconception that neonatal care is difficult and expensive [9].

During the neonatal period, perhaps more than at any other time, there are deep rooted health practices and beliefs. These differ in different communities but often share common themes. Hot bed use, food avoidance in the mother postpartum, discarding colostrum and application of various substances to the umbilical cord (such as cow dung, petrol and ash) are examples of widely held practices [10-12]. Many of these practices are potentially harmful to the neonate and need to be addressed in the communities where they occur by community engagement and education.

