### **Perinatal Mortality**

The expected outcome of the SBLP is a reduction in perinatal mortality (PMR). In order to assess the effectiveness of the SBLP an accurate measure of PMR is needed. Although births and deaths are required to be registered in Cambodia, often the births and deaths of young infants, particularly those born at home, are not registered. To accurately determine the perinatal mortality rate (PMR) in PVH province, government village health support groups (VHSG) will be asked to record details of all births and neonatal deaths in their villages. The data collected will include:

1. Village name
2. Estimated Date of Delivery
3. Date of delivery
4. Gender
5. Prematurity
6. Place of delivery
7. Birth weight
8. Alive at 28 days

The data will be brought to monthly VHSG meeting and entered in to a database by a member of the SBLT. Each VHSG will receive a \$2 phone credit card for each completed birth data collected. If a neonate dies, a verbal autopsy will be performed by one of the Saving Babies Lives team using the WHO Verbal autopsy tool [23].

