## **4. OBJECTIVES AND OUTCOME MEASURES**

Objectives	Outcome Measures	Time point(s) of evaluation of this outcome measure (if applicable)
Primary Objective The design, implementation and assessment of a comprehensive community neonatal health package utilising medical and social interventions	A comprehensive community neonatal health package utilising medical and social interventions	Study end
Secondary Objective Reduction of perinatal mortality in PVH province, Cambodia	A one third reduction in perinatal mortality in PVH province, Cambodia	Study end
Tertiary Objectives: To describe the characteristics of neonates born in PVH province, Cambodia over a five-year time period	A document that describes characteristics of neonates, born in PVH province, Cambodia over a five-year time period	Study end
To develop a tool to undertake a full review of neonatal services and capabilities in PVH province, Cambodia 
 
a. Assess the level of knowledge possessed by health care workers with respect to fundamental areas of care surrounding delivery and the neonatal period
 
b. Evaluate current practice regarding delivery and neonatal care
 
c. Undertake a review of health centre facilities and resources
 
d. Record the staff composition and working patterns
 
e. Detect commonalities as well as differences between facilities
 
f. Assess the local community service provision, including the activity of the VHSGs as well as any other community health projects and initiatives
 
	A user-friendly tool to assess neonatal healthcare services A report detailing neonatal services and capabilities in PVH province, Cambodia	Study end

g. Identify factors that may be functioning as barriers and facilitators to improvements in the delivery of care
		

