#### **Secondary Outcomes:**

1. Description of the cohort
  - a. Prematurity
  - b. Birth weight
  - c. Sex
2. Facility based deliveries

Facility based deliveries prematurity, sex, will be described using percentage and compared between groups using Chi-square test or Fisher's exact test as appropriate. Number of ANC visits will be described using median with inter-quartile range (IQR) and compared between groups using Mann-Whitney U test. Birth weight will be described using mean with standard deviation and compared between groups using Student's t test or using median with inter-quartile range and compared between groups using Mann-Whitney U test if data have non-normal distribution.

Statistical analysis will be performed using STATA software package. Statistical significance will be considered if  $p$ -value  $< 0.05$

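### Perinatal mortality, a proportion of births, is planned as a hazard rate, so stillbirths and day-of-birth deaths can be lost or mis-weighted

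*Protocol*

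**What the plan says.** Protocol section 8.1 (Perinatal Mortality, Primary Outcome) sets the measure: "Perinatal mortality rate will be described by hazard rate and 95% confidence interval (CI) separated by groups". The between-group test follows: "Log-rank test will be used for univariate comparison of survival". So does a further summary: "We will also describe median time to perinatal death with 95% CI in each group from Kaplan-Meier plot".

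Section 4 lists mortality as the secondary objective of the study, with the outcome measure "A one third reduction in perinatal mortality in PVH province, Cambodia".

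Section 3.2 (Perinatal Mortality) describes the data source. Village health support group workers "will be asked to record details of all births and neonatal deaths in their villages". The listed items include the date of delivery, without a clock time, and a single survival item, "Alive at 28 days". The list has no stillbirth item and no date of death. A verbal autopsy follows a neonatal death.

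The protocol does not define perinatal death, does not mention stillbirth, and gives neither a time origin for the survival analysis nor a rule for deaths at time zero. Section 8.1 refers to the SAP for full details; the SAP was not available for this review.

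**The concern.** The named outcome and the stated measure are different quantities. A perinatal mortality rate, as the term is conventionally used, divides stillbirths plus early neonatal deaths by total births. A hazard divides deaths by person-time.

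The mismatch matters because of when perinatal deaths occur. If the clock starts at birth, a stillborn infant is never at risk, and an infant who dies on the date of delivery has a recorded time of zero. These are the deaths around delivery that the programme's training and resuscitation equipment are aimed at (sections 3 and 4). A time-from-birth analysis needs a special rule for them; a proportion of births does not. Without the rule, the result depends on how an analyst or a program treats such records.

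The planned Kaplan-Meier median has a separate problem: it exists only if the survival curve falls to 50%.

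**Working it through.** The protocol gives no perinatal mortality rate, event count or power for this outcome, so there is no stated figure to reproduce. Three checks follow.

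**1. Share of deaths with no survival time**

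Inputs:
- f, the first-day share of neonatal deaths. Section 3 says: "It is estimated that 2.9 million neonates die each year, with one million of these occurring on the first day of life". So f = 1.0/2.9 = 0.345, about 34%.
- e, the share of neonatal deaths that fall in the first week. Not in the protocol; assumed 0.65 to 0.85. Setting e = 1 counts all deaths to 28 days.
- r, stillbirths per early neonatal death. Not in the protocol; assumed 0 to 1.5.

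Zero-time share of perinatal deaths = (r·e + f) / ((1 + r)·e).

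Example with e = 0.75 and r = 1: (0.75 + 0.345) / 1.5 = 0.73.

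| r | e = 0.65 | e = 0.75 | e = 0.85 | e = 1 |
|---|---|---|---|---|
| 0 | 53% | 46% | 41% | 34% |
| 0.5 | 69% | 64% | 60% | 56% |
| 1 | 77% | 73% | 70% | 67% |
| 1.5 | 81% | 78% | 76% | 74% |

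The share reaches 50% at r = 1 − 2f/e. This is r = 0.08 for e = 0.75 and r = 0.31 for e = 1; for e = 0.65 the share is already above 50% at r = 0.

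The table treats the first day of life as the calendar date of delivery. If it means 24 hours, some of these deaths fall on the next date and have time 1. Suppose half do, so f = 0.172. With e = 0.75 the share becomes (0.375 + 0.172)/1.125 = 49% at r = 0.5 and (0.75 + 0.172)/1.5 = 61% at r = 1.

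**2. Hazard against proportion**

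Illustration per 1,000 births, all assumed: 30 perinatal deaths, r = 1, e = 0.75, 7 days of complete follow-up, and 3 days contributed by each later first-week death.

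- Neonatal deaths: 30/(2 × 0.75) = 20. Stillbirths: 15. First-day deaths: 0.345 × 20 = 6.9. Later first-week deaths: 15 − 6.9 = 8.1.
- Person-time: 970 × 7 + 8.1 × 3 = 6,814 baby-days.
- Proportion: 30 per 1,000 births.
- Hazard with zero-time deaths kept: 30/6,814 = 4.4 per 1,000 baby-days. Giving each of them half a day also yields 4.4.
- Hazard with zero-time deaths dropped: 8.1/6,814 = 1.2 per 1,000 baby-days, with about 8 of 30 deaths left.

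The same births thus give hazards that differ almost fourfold.

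For the relative effect, take a comparison arm with 20 deaths per 1,000, a one-third reduction (risk ratio 20/30 = 0.67).
- If the reduction is spread evenly over the three types of death, the hazards are 2.91 against 4.40 with zero-time deaths kept, and 0.79 against 1.19 with them dropped. Both ratios are 0.66.
- If, at the extreme, all 10 averted deaths are zero-time deaths, person-time is 980 × 7 + 24.3 = 6,884. With these deaths kept, the hazard is 20/6,884 = 2.91 and the ratio is again 0.66. With them dropped, it is 8.1/6,884 = 1.18 and the ratio is 0.99.

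**3. Median time to perinatal death**

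A Kaplan-Meier median requires 500 deaths per 1,000 births. At assumed rates of 20 to 40 per 1,000, survival at day 7 is 96% to 98%, so neither the median nor its CI is estimable. A median among the deaths alone could be computed, but it would not be a Kaplan-Meier estimate for the group.

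**The case against.** The best defence is that time zero does not by itself remove a death. Such a death still counts in the numerator of a hazard, and a Kaplan-Meier curve can step down at time 0. With every death kept and short, complete follow-up, the Kaplan-Meier failure proportion equals deaths per birth, and the hazard ratio is close to the risk ratio, as the second check shows. The time origin and the rule for zero-time records may also sit in the SAP. This stands, and it rules out three stronger readings that a reader might infer.

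- *The plan as written discards most perinatal deaths.* The protocol contains no instruction to drop zero-time deaths and states no time origin. Its only relevant figure is about 34% of neonatal deaths on the first day; any majority depends on assumed stillbirth and first-week shares.
- *The named software will drop them.* The protocol says only: "Statistical analysis will be performed using STATA software package". It says nothing of how records with zero time would be set up or treated.
- *The result could not be compared with the one-third target.* That target is a relative reduction. A hazard ratio that retains all deaths would be close to the risk ratio.

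It can also be said that stillbirths enter only through the conventional meaning of perinatal, since the protocol never mentions them. That is true, but it does not rescue the measure: with no stillbirths counted, the zero-time share is still 34% to 53% in the table.

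The defence does not remove the central point. The hazard rate, log-rank test and median are positive choices in section 8.1, not details left open, and an SAP that follows the protocol would inherit them.

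**Conclusion.** The point holds as a misfit between outcome and measure. The protocol calls the outcome a perinatal mortality rate and then expresses it per unit of person-time. On the natural but unstated reading that time runs from birth, stillbirths have no time at risk and deaths on the delivery date have time zero. A large share of deaths can therefore be lost or mis-weighted, depending on handling.

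From the protocol's own figure, that share is about 34% of neonatal deaths, if first day means the delivery date. With stillbirths counted at 0.5 to 1.5 per early neonatal death and a first-week share of 65% to 85%, it is 60% to 81% of perinatal deaths. Those inputs are assumed, and the range falls if some first-day deaths carry the next calendar date. Possibly most is as far as the evidence goes.

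That the Kaplan-Meier median will not be reached needs none of these assumptions, only that perinatal mortality is far below 50%.

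**What to change.** In section 8.1, define the outcome as perinatal deaths (stillbirths plus deaths before 7 completed days) per 1,000 total births in each arm. Give a between-arm risk ratio or risk difference with a 95% CI that allows for clustering by health-centre administrative group, the unit defined in section 5.

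Drop the Kaplan-Meier median. If a survival curve is kept, present it as a description of age at death in live births only, and state how day-of-birth deaths are timed, for example at half a day.

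In section 3.2, add stillbirth status and date of death to the listed birth data. Without them the outcome cannot be derived from the listed items: a yes/no status at 28 days does not separate first-week from later deaths. The verbal autopsy may supply age at death for neonatal deaths, but the protocol does not say so.

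The cost is a wording change in the protocol and SAP plus two extra fields on an existing form. A binary outcome is simpler to derive than a survival time.

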#### **Sample size Calculation**

With perinatal mortality rate and a simple parallel cluster randomised trial design, the number of clusters are fixed to the intervention and control arm clusters and the time-frame is fixed to five years. The change in study design has been necessitated by logistical reasons and the post-study power calculations are not relevant. We will report limitations to the power in write-up.

The statistical analysis will remain broadly the same, with the main difference being that we will no longer adjust for the confounding effects of time. The primary analysis will exclude pilot cluster results, and will only be conducted on the intervention and control arm clusters.

Please see the study Statistical Analysis Plan for full details.

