### ***Economic Evaluation***

A detailed cost analysis will be carried out to estimate the added resources that are required for the SBLP as compared with standard care. These costs will be combined with estimates for the incremental cost of caring for neonates at the referral hospital if attendance is found to increase, and by modelling the subsequent survival benefits in terms of incremental disability adjusted life years averted. This will indicate whether SBLP are cost-effective as compared to the normal standard of care (control arm).

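### The protocol fixes the mortality comparison as per-arm hazard rates and a log-rank p-value, with no between-arm estimate and interval and no stated allowance for clustering

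*Protocol*

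**What the plan says.** Protocol section 8.1, Perinatal Mortality, Primary Outcome, lists four outputs:

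- a rate per arm: "Perinatal mortality rate will be described by hazard rate and 95% confidence interval (CI) separated by groups";
- a plot: "Survival between groups will also be described using Kaplan-Meier plot";
- a test: "Log-rank test will be used for univariate comparison of survival";
- a median per arm: "We will also describe median time to perinatal death with 95% CI in each group from Kaplan-Meier plot".

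The significance rule comes at the end of the Secondary Outcomes text: "Statistical significance will be considered if" the p-value is below 0.05.

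The outcome measure in the Synopsis and in section 4 is a size of effect: "A one third reduction in perinatal mortality in PVH province, Cambodia". Section 5 describes a cluster randomised design. The Economic Evaluation text in section 8.1 relies on "modelling the subsequent survival benefits in terms of incremental disability adjusted life years averted", with the control arm as comparator.

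Under Sample size Calculation the protocol says that "the post-study power calculations are not relevant", that the analysis is largely unchanged apart from dropping the adjustment for time, that pilot clusters are left out of the primary analysis, and that the SAP holds the full details.

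**The concern.** The section does not leave the mortality analysis open. It sets it out item by item, and the items do not match the stated outcome. Both intervals are per arm. The only between-arm quantity is a p-value, and a log-rank test asks whether the arms differ, not by how much. No section of the protocol names a rate ratio, hazard ratio, risk ratio or risk difference.

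Nothing in the list allows for clustering either. A plain log-rank test treats births as independent, whereas births within a health-centre group share staff, facilities and the intervention itself.

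At stake is whether the headline mortality result answers the question the protocol sets, and whether its precision is stated correctly. The economic model also needs the size of the survival benefit.

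**Working it through.** **Plan's own figure.** The protocol gives no power or event calculation for mortality, so there is nothing to reproduce.

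**What the listed outputs supply**

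| Output | Between arms? | Interval? |
|---|---|---|
| Hazard rate | No, per arm | Yes, per arm |
| Kaplan-Meier plot | Visual only | None stated |
| Log-rank test | Yes | No, p-value only |
| Median time to death | No, per arm | Yes, per arm |

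At the mortality assumed below (20 to 40 per 1,000), a Kaplan-Meier curve over all births never falls to 50%, so its median cannot be estimated. The arm rates are then the only usable outputs with an interval.

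**Inputs from the protocol**
- 28 health centres and about 5,300 deliveries a year (section 3.3).
- 4 pilot clusters, 10 intervention clusters, the rest control; October 2019 to December 2022, which is 39 months or 3.25 years (section 5).

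**Assumptions not in the protocol**
- One cluster per health centre, so 28 − 4 − 10 = 14 control clusters, all of equal size.
- Control mortality of 30 per 1,000, with 20 and 40 as a range.
- Design effect (DE) of 1, 2 or 4.
- Observed intervention-to-control ratio of 0.667.

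**Births and deaths**
- Births per cluster: 5,300/28 × 3.25 = 615.2, giving about 6,152 intervention and 8,613 control births.
- Deaths: 6,152 × 0.020 = 123 and 8,613 × 0.030 = 258.

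**Crude ratio from the arm rates**

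SE(log ratio) = √[DE × (1/123 + 1/258)] = 0.110 × √DE. The 95% interval is 0.667 × exp(±1.96 × SE).

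| DE | Intervention rate per 1,000 | Control rate per 1,000 | SE | Interval for ratio | p |
|---|---|---|---|---|---|
| 1 | 20.0 (16.8–23.9) | 30.0 (26.6–33.9) | 0.110 | 0.54–0.83 | 0.0002 |
| 2 | 20.0 (15.6–25.7) | 30.0 (25.2–35.6) | 0.155 | 0.49–0.90 | 0.009 |
| 4 | 20.0 (14.0–28.5) | 30.0 (23.5–38.3) | 0.219 | 0.43–1.02 | 0.06 |

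At 20 per 1,000 the interval is 0.51–0.87 (DE 1) or 0.39–1.13 (DE 4). At 40 per 1,000 it is 0.55–0.80 or 0.46–0.97.

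**Cross-check with between-cluster variation**

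Using a between-cluster coefficient of variation k, with d₁ = 12.3 and d₀ = 18.5 deaths per cluster and t on 22 degrees of freedom: SE = √[(k² + 1/d₁)/10 + (k² + 1/d₀)/14].

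- k = 0.2: SE 0.137, interval 0.50–0.89.
- k = 0.3: SE 0.166, interval 0.47–0.94.

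The variance ratios to the DE 1 case are (0.137/0.110)² ≈ 1.6 and (0.166/0.110)² ≈ 2.3. A design effect of 4 therefore sits at the high end: solving 1 + k²d = 4 gives k of about 0.5 (intervention) and 0.4 (control).

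**Why the p-value alone is not enough**

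At 30 per 1,000 and DE 1, an observed 20% reduction gives p = 0.03 (0.65–0.98), although the point estimate falls short of one third. At DE 4, an observed reduction of exactly one third gives p = 0.06.

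**The case against.** The strongest objection is that an effect measure is the kind of detail a protocol leaves to its SAP, and this protocol points there. The text also hints at a model beyond the list: the log-rank test is called univariate, and the redesign is said to remove an adjustment for time that none of the listed items makes. The SAP may therefore hold a proper contrast. This stands as a limit: the point concerns what the protocol's own text fixes, not the trial's whole analysis.

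A reader might infer several stronger things that the protocol does not support:

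- **That the analysis cannot show whether one third was reached.** Two independent arm rates with intervals do yield a crude ratio and interval, as shown above. What is unstated is whether those arm intervals allow for clustering.
- **That cost per DALY would carry no sampling uncertainty.** The Economic Evaluation text does not say how uncertainty enters the model.
- **That p below 0.05 would be taken as meeting the target, or p above 0.05 as no effect.** The protocol has no such rule, and it promises to report limits to power.
- **That the computed intervals measure the defect.** They show how imprecise the trial would be under assumed inputs, whether or not a ratio is reported.

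The one-third target is also stated for the province without saying whether it is arm against arm or before against after. A ratio of 0.667 is the benchmark only under the first reading.

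**Conclusion.** The point holds on the protocol text. Section 8.1 lists per-arm rates and a univariate log-rank p-value for an outcome defined as a size of reduction in a cluster randomised trial, and it names neither a between-arm estimate with an interval nor an allowance for clustering. The crude ratio that can be derived is only as sound as the arm intervals. In the illustration its upper limit moves from 0.83 to 1.02 between design effects of 1 and 4, and reaches 0.89 to 0.94 at coefficients of variation of 0.2 to 0.3. Those figures rest on assumed mortality, equal clusters, one cluster per health centre and assumed between-cluster variation; the mismatch between the listed analysis and the stated outcome does not. The change should be made, but it corrects the specification and does not show that the trial is unable to answer its question.

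**What to change.** In section 8.1, Perinatal Mortality, Primary Outcome:

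1. Make the main result the intervention-to-control ratio of the mortality outcome actually recorded, with the absolute difference per 1,000 births. Give each a 95% interval from a cluster-level or cluster-adjusted analysis of the intervention and control clusters. The outcome needs naming with care: the data list in section 3.2 covers births and neonatal deaths and survival to 28 days, with no explicit stillbirth field, so perinatal deaths per total births may not be obtainable from it.
2. Take the p-value from that same analysis in place of the plain log-rank test.
3. State in sections 1 and 4 whether the one-third reduction is intervention against control or before against after, and read the matching interval against it.
4. Use the same estimate and interval in the DALY model.
5. If the SAP already defines the contrast, align the protocol text with it.

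The cost is a change of wording. Intervals will be wider than unadjusted ones, by √DE on the log scale, which reflects the clustering in the design.

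The new text could read: the primary mortality comparison is the ratio, and the difference per 1,000 births, of the recorded mortality outcome between intervention and control clusters, each with a 95% confidence interval that allows for clustering.

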## 5. STUDY DESIGN

A cluster randomised study design will be used, with a cluster being defined as a HC administrative group, as defined by the PVH Provincial Health Department. This includes all HC, HP, villages, and villagers in that group.

Pilot: to begin in July 2018, consisting of 4 clusters.

Intervention arm: to begin October 2019, consisting of 10 clusters.

Control arm: all remaining clusters.

Completion: December 2022.

The SBLP will be introduced into the provincial referral hospital during 2018.

The SBLP will be introduced into the new referral hospital during 2022.

The choice of which health centres will be included at each time point will be made using purposive sampling to ensure a mix of health centre characteristics. Characteristics that will be taken into account are the distance from the health centre to the referral hospital and number of villages the HC serves.

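### The named between-arm tests treat births as independent although whole health-centre groups are allocated, so p-values will be too small and mortality confidence intervals too narrow

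*Protocol*

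**What the plan says.** Section 5 sets the unit of allocation: "A cluster randomised study design will be used, with a cluster being defined as a HC administrative group", including all its facilities, villages and villagers. The arms are given as "Intervention arm: to begin October 2019, consisting of 10 clusters" and "Control arm: all remaining clusters". Four further clusters form a pilot ("Pilot: to begin in July 2018, consisting of 4 clusters") and are left out: "The primary analysis will exclude pilot cluster results, and will only be conducted on the intervention and control arm clusters".

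Section 8.1, under Perinatal Mortality, plans a hazard rate with a 95% confidence interval per group, Kaplan-Meier curves, and a median time to death with its interval. It names one comparison between arms: "Log-rank test will be used for univariate comparison of survival". Under Secondary Outcomes, facility delivery, prematurity and sex "will be described using percentage and compared between groups using Chi-square test" or Fisher's exact test. Antenatal visits get a Mann-Whitney test, and birth weight a t test or Mann-Whitney test. Significance is set at p < 0.05.

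The Sample size Calculation text adds: "The statistical analysis will remain broadly the same, with the main difference being that we will no longer adjust for the confounding effects of time". It then refers to the SAP for full details. The protocol mentions no intracluster correlation, random effect or frailty, GEE, cluster-robust variance or cluster-level summary. In the analysis section, clusters appear only in the intention-to-treat rule, in the remark that their number is fixed, and in the exclusion of the pilot.

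**The concern.** Births in one health-centre group share staff, distance to the referral hospital and village health workers, so their outcomes are likely to be correlated. The tests named take their variance from the number of births, as if each birth had been allocated separately. They omit the between-cluster part of the variance, which shrinks only as clusters are added, not as births are added.

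The consequence is a false-positive rate above the stated 5% on the mortality comparison, and mortality intervals that claim more precision than the design can give. The central hypothesis is a significant effect on neonatal mortality, and the programme is meant to be taken to other parts of Cambodia. A p-value from the log-rank test could support roll-out of a package that does nothing.

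**Working it through.** **The plan's own figures.** The protocol gives no power, ICC, baseline mortality or design effect to reproduce. Its only sample-size arithmetic is a headcount, 5 × 5,300 = 26,500 births, which is correct.

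**Inputs from the protocol.** 28 health centres and about 5,300 deliveries a year (section 3.3); 4 pilot and 10 intervention clusters, intervention start October 2019, completion December 2022 (section 5).

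**Assumptions.** One cluster per health centre, so 28 − 4 − 10 = 14 control clusters; equal cluster sizes; births counted over the 39 months from October 2019 to December 2022; two-sided 5% level. ICC and mortality are not given, so ranges are shown.

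**Cluster size.** m = 5,300/28 × 39/12 = 615.2 births. The analysis set is 24 × 615.2 ≈ 14,764 births.

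**Formulas.** Design effect DE = 1 + (m − 1) × ICC. Correct interval width relative to the naive one = √DE. True type I error of a nominal 5% test = 2 × [1 − Φ(1.96/√DE)].

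Example for ICC 0.001: DE = 1 + 614.2 × 0.001 = 1.61; √DE = 1.27; 1.96/1.27 = 1.54; type I error = 12.3%.

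| Assumed ICC | Between-cluster CV at 3% mortality | DE | Interval width ratio | True type I error |
|---|---|---|---|---|
| 0.0005 | 0.13 | 1.31 | 1.14 | 8.6% |
| 0.001 | 0.18 | 1.61 | 1.27 | 12.3% |
| 0.002 | 0.25 | 2.23 | 1.49 | 18.9% |
| 0.005 | 0.40 | 4.07 | 2.02 | 33.1% |

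The CV column is √[ICC × (1 − p)/p] with p = 0.03.

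**Simulation check.** 20,000 null trials per setting were run with 10 against 14 equal clusters, beta-binomial deaths and mortality of 2%, 3% or 4%. A two-proportion test that ignores clusters stood in for the log-rank test. Over the four ICCs it rejected in 8.2% to 33.0% of null trials. With ICC = 0 it rejected in 4.9% to 5.1%, so the excess comes from clustering alone. A t test on the 24 cluster rates rejected in 4.7% to 5.1% throughout.

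**Sensitivity.** Counting five years of births (26,500/28 = 946 per cluster), the same ICCs give 10.6% to 41.3%. For other outcomes, an assumed ICC of 0.01 or 0.05 at m = 615 gives DE = 7.14 or 31.71 and a type I error of 46% or 73%. Unequal cluster sizes would increase the inflation.

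**The case against.** The strongest reply is that section 8.1 is not the whole analysis. It points to a SAP that is not at hand, and modelling of clustering is often left to that document. The log-rank test is called univariate, and the rest of the mortality text is descriptive. The statement that time will no longer be adjusted for suggests an earlier model, since none of the listed tests adjusts for time. A paper on intracluster correlation stands in the reference list, although the text shown does not cite it.

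This means that a cluster-adjusted model may exist. It does not rescue the protocol, which does not stay silent: it names the between-arm tests, names no other for mortality, and does not say that a different model decides.

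Four narrower points stand:

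- Intervals are planned only for the per-group mortality summaries, so for the secondary outcomes the problem concerns p-values.
- Prematurity, birth weight and sex are listed as description of the cohort. The matter weighs most for mortality and facility delivery.
- The size of the error rests on ICC values that the protocol does not supply. At the low end the type I error is about 9%, not a multiple of several times nominal.
- The 5% held by the cluster-level t test assumes exchangeable clusters. Section 5 chooses health centres purposively, and no variance correction removes bias from that choice.

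**Conclusion.** The concern holds. Allocation is by health-centre group, the comparative tests named in section 8.1 assume independent births, and nothing in the protocol accounts for clustering. If these tests carry the inference, the true type I error of the mortality comparison is about 9% to 33% for ICCs from 0.0005 to 0.005, and correct intervals are 1.14 to 2.02 times as wide.

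These figures are illustrative, since they rest on the assumed ICCs, 28 single-centre clusters of equal size, and 39 months of births. The direction does not depend on them: with about 615 births per cluster, the error is negligible only if the ICC is practically zero. This must be corrected before the mortality comparison is made.

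**What to change.** In section 8.1, replace the log-rank test as the between-arm mortality test with an analysis that respects the clusters. Either of these would do:

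- a t test or weighted regression on the cluster-level mortality rates (24 clusters and 22 degrees of freedom under the assumption above);
- a mixed-effects or GEE Poisson or binomial model with cluster as the grouping unit and a small-sample correction for about 24 clusters.

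Report the between-arm rate ratio and its confidence interval from that analysis, and keep the Kaplan-Meier curves as description. Use the same approach for facility delivery and for any between-arm p-value on prematurity, birth weight or antenatal visits. If the SAP already specifies such a model, section 8.1 should say that it governs and that the listed tests are descriptive only.

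The cost is a change of wording in section 8.1 and, where needed, the SAP; no new data are required. Intervals will widen and the honest power is lower. For a one-third reduction from an assumed 3% mortality, power is 97% under independence but about 92%, 85%, 72% and 46% at ICC 0.0005, 0.001, 0.002 and 0.005 (normal approximation with the numbers divided by the design effect). That belongs with the power limitations the protocol already undertakes to report.
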